1.1.2 Secondary Objectives

- To compare the diagnostic accuracy of FLT PET/CT with that of FDG PET/CT as indicators of tumor response to therapy
- To evaluate whether FLT tumor uptake either prior to therapy and/or following completion of therapy are independent predictors of complete response to therapy
- To evaluate whether there is a significant difference in tumor, selected normal organs, and mediastinal blood pool FLT dynamic influx parameter (Ki), SUV at 1 hours and 2 hours post injection
- To estimate the diagnostic accuracy of percent change in SUV between pre-treatment and mid-treatment FLT PET/CT as an indicator of complete response to therapy

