5.1.1 For subjects enrolling in early response arm

- Participants in this arm will undergo a pre-treatment FLT PET/CT and FDG PET/CT (+/- 2 weeks of each other) imaging prior to beginning lymphoma therapy.
- They will then continue in a lymphoma therapy trial at the NIH Clinical Center or receive a new course of treatment at their home institution.
- Repeat FDG and FLT PET/CT studies will be performed following 2 cycles of chemotherapy.
 - The FDG PET/CT study should be performed as close as possible (i.e. within 4 days) before the subsequent cycle; for example, on days 17 to 21 of a 21-day cycle.
 - The repeat FLT PET/CT imaging should be performed within +/- 2 weeks of the FDG PET/CT study.
- Post treatment FDG and FLT PET/CT studies will be performed
 - The FDG PET/CT study will be performed ≥ 3 weeks after the completion of chemotherapy
 - The FLT PET/CT scan will be performed within +/- one week of the 3rd FDG PET/CT.
- Patients in this arm with residual FDG positive mass following completion of therapy may be enrolled in the residual mass arm.
- The target lesion will be defined as the hypermetabolic (uptake > background) lesion ≥ 1 cm with the highest SUV_{max} at 1 hour post injection
- Primary analyses will be performed on the target lesion and compared with complete response (CR or Cr_u, [Table 6](#)).

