5.5.2 General image parameter extraction

- FLT and FDG uptake greater than surrounding background will be considered positive.
- The “target” will be identified, as a lesion $\geq 1\text{cm}$ with the highest SUV (amongst all identified hypermetabolic lesions).
- All regions/volumes of interest will be saved as DICOM-RT structure sets. Region volumes, and SUV values will be output to an Excel spreadsheet using MIMVista imaging software (www.mimvista.com)
- For the hypermetabolic lesions, an estimated smoothed maximum SUV (SUV_{max}) will be reported as the mean SUV value of an automated 85% maximum pixel value threshold based volume of interest (i.e. the average SUV of the “hottest” 15% of pixels in the user defined lesion). This method reduces the chances of the SUV_{max} value being dominated one or more “noisy” pixel values.
- All lesions will be followed from baseline with the same lesion number, even if they have resolved.
- For quality control, mediastinal and left ventricular blood pool (BP) SUV means, spleen, and liver SUV mean will be measured in all FLT and FDG scans.
 - To measure the left ventricular cavity BP SUV_{mean} , the mean SUV of a 1 cm spherical volume of interest (VOI) will be placed in the left ventricular cavity, avoiding the myocardial wall
 - For liver and spleen SUV_{mean} , a spherical VOI of 2 to 5 cm in diameter will be placed in a homogeneous area in the center of the organ (excluding the central hilum of the liver), and the mean SUV recorded.
- For the FLT images, the K_i Patlak influx parameter will be extracted from the 60 minute dynamic data. SUV values (corrected for the fraction of unmetabolized FLT (as

determined by thin layer chromatography (TLC)) will be recorded for the 1- and 2- hour static images.

- For the primary analyses, the 1- hour SUV (SUV₁) parameters will be used
- For the FDG images SUV values will be recorded for the 1 hour static images.
- On transmission CT, lesion dimensions will be determined in perpendicular planes where the lesion appears largest.

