5.5.3 Early response arm

- The percent of decrease or increase in SUV uptake in post cycle 2 and end of treatment scans in comparison with baseline scans will be calculated as follow:

$$\frac{\text{SUV}_{\text{max}} \text{ post cycle 2 or end of treatment} - \text{baseline SUV}_{\text{max}}}{\text{Baseline SUV}_{\text{max}}}$$

Table 3 Image Analysis Parameters for Early Response Arm

Pre-treatment	Mid-treatment	Post Treatment
FLT (K _i , SUV ₁ , SUV ₂)	FLT (K _i , SUV ₁ , SUV ₂)	FLT (K _i , SUV ₁ , SUV ₂)
FDG (SUV ₁)	FDG (SUV ₁)	FDG (SUV ₁)
CT (bidirectional measurements)	CT (bidirectional measurements)	CT (bidirectional measurements)

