8.1.2 Secondary Objectives

- 2.a.To compare the diagnostic accuracy of FLT PET/CT with that of FDG PET/CT as an indicator of tumor response to therapy
- 2.b. To evaluate whether FLT tumor uptake prior to therapy or following completion of therapy are independent predictors of complete response to therapy
- 2.c. To evaluate whether there is a significant difference in tumor, selected normal organs ,and mediastinal blood pool FLT dynamic influx parameter (Ki),SUV at 1 hours and 2 hours post injection

- 2.d To estimate the diagnostic accuracy of percent change in SUV between pre-treatment and mid-treatment FLT PET/CT with regard to complete response to therapy

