8.1.3 Analysis Plan

For the primary analyses, sensitivity and specificity will be estimated and 95% confidence intervals provided. Subjects with an FLT SUV greater than mediastinal blood pool activity will be considered FLT positive. In the early response arm, subjects with complete response (CR or Cr_u, **Table 6**) as determined by the CHESON revised response criteria will be considered disease negative (all others will be considered disease positive). In the residual mass arm, subjects with any malignant cells on biopsy will be considered disease positive.

For secondary objectives 2a and 2d, empirical ROC curves will be estimated, along with non-parametric AUCs and corresponding 95% confidence intervals. For 2b, we will evaluate the ability of FLT to predict clinical response independent of other known predictors using logistic regression. For aim 2c, we will test for differences using signed-rank tests.

No stratification based on lymphoma histology or treatment is planned due to the small amount of expected variability in treatments available.

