8.1.4 Sample size

We plan to enroll 40 participants in the first arm and 30 participants in the residual tumor arm.

In the first arm, we assume that patients enrolled in this trial come from a randomized trial of DA-EPOCH-R vs. R-CHOP. With DA-EPOCH-R treatment, the expected response rate is 74%(92), while with R-CHOP it is 50%. (21). If we assume half of the patients enrolled in this trial will receive DA-EPOCH-R and the other half will receive R-CHOP, the average response rate is 62%, which will provide about 25 responders, who will contribute to estimates of sensitivity. About 15 patients will be non-responders and will contribute to estimates of specificity. The lower bounds for sensitivity are given in **Table 7**. Lower bounds for specificity are given in **Table 8**.

For the second primary objective, we assume that the 50% of patients with FDG positive residual disease will have positive pathology.(93) This provides 15 positives and 15 negatives. **Table 8** provides lower bounds for confidence intervals for sensitivity and specificity for this objective.

The following table provides expected lower bounds for 95% confidence intervals given observed values of sensitivity and specificity for a sample size of 15. We anticipate sensitivity and specificity to be about 85% and 90%, respectively. Hence, the sample size will provide lower bounds above the chance threshold of 50%.

Table 7

Sensitivity (n=25)	Expected lower bound of exact 95% CI
20/25(=.80)	0.59
21/25(=.84)	0.64
22/25(=.88)	0.69

Table 8

Sensitivity/Specificity (n=15)	Expected lower bound of exact 95% CI
12/15 (=0.8)	0.52
13/15 (=0.87)	0.60
14/15 (=0.93)	0.68

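### Objective 2b fits an adjusted logistic model to about 15 non-responders without naming estimator, covariates or a rule for two scans; the FLT odds ratio would probably be overstated and the false-finding rate moderately raised.

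*Combined protocol and SAP*

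**What the plan says.** Section 1.1.2 gives the objective as "To evaluate whether FLT tumor uptake either prior to therapy and/or following completion of therapy are independent predictors of complete response to therapy". Section 8.1.2 repeats it with a plain alternative: "To evaluate whether FLT tumor uptake prior to therapy or following completion of therapy are independent predictors of complete response to therapy". The only analysis text is one sentence in 8.1.3: "For 2b, we will evaluate the ability of FLT to predict clinical response independent of other known predictors using logistic regression". It does not list the known predictors. It also does not say how the model is fitted, which test is used and at what level, whether the two scans are modelled separately or together, or how two results would be combined.

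The FLT measure is open as well. Section 5.5.2 fixes it only for the main analyses ("For the primary analyses, the 1- hour SUV"), while "Table 3 Image Analysis Parameters for Early Response Arm" lists Ki, 1-hour SUV and 2-hour SUV at each time point.

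On numbers, 8.1.4 says "We plan to enroll 40 participants in the first arm and 30 participants in the residual tumor arm" and, for the first arm, "About 15 patients will be non-responders".

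On timing of the post-treatment scan, 5.1.1 says "The FLT PET/CT scan will be performed within +/- one week of the 3rd FDG PET/CT"; footnote a to Table 5 in 6.1 allows two weeks either side. Table 6 in 7.2.1 uses PET status after treatment to define complete response.

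**The concern.** There are three separate problems.

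- **Estimation.** Maximum-likelihood logistic regression is biased away from the null when the smaller outcome class is small relative to the number of coefficients. About 15 non-responders is small even for two or three coefficients. The reported odds ratio for FLT would tend to look stronger than it is.
- **Multiplicity.** Two scans are named and a positive result on either would satisfy the wording. With no rule, the chance of at least one false finding exceeds the level of each test. Unnamed covariates and an unnamed FLT measure leave room for more attempts.
- **Interpretation.** Post-therapy FLT is done within a week or two of the FDG scan that informs the response call. It is measured at about the same time as the outcome, so an association with it is not a prediction.

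At stake is how a secondary result would be read: an inflated odds ratio reported as independent predictive value.

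**Working it through.** **The plan's own figures (8.1.4).** The average response rate is (0.74 + 0.50)/2 = 0.62. Responders: 40 x 0.62 = 24.8, about 25. Non-responders: 40 x 0.38 = 15.2, about 15. These reproduce. No alpha, power or error rate is given for 2b.

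**Non-responders per coefficient** (intercept excluded, one FLT term):
- 1 covariate: 15/2 = 7.5
- 3 covariates: 15/4 = 3.75
- 5 covariates: 15/6 = 2.5

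**Bias of the FLT coefficient.** Simulation with n = 40, baseline response 62% and an assumed true log-odds of 1.0 per SD (odds ratio e^1.0 = 2.72):

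| Covariates | Mean overstatement, maximum likelihood | Implied odds ratio |
|---|---|---|
| 1 | about 17% | e^1.17 = 3.22 |
| 3 | about 31% | e^1.31 = 3.71 |
| 5 | about 49% | e^1.49 = 4.44 |

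The Firth estimate was off by about 1-7% in the same settings. A repeat with 4,000 trials per setting and covariate log-odds of 0.4 to 0.5 per SD gave mean overstatements of about 14-17%, 27-30% and 43-60%. The spread depends on covariate strength and on how near-separated data sets are handled. The means are pulled up by a few very large estimates: the median overstatement was about 7-9%, 16-17% and 28-30%.

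**False findings with no true FLT effect.** Assumptions: two-sided 5% per test; independent covariates with log-odds 0.5 per SD; modest correlation between the two scans (0.3 component); 4,000 runs. For two independent exact tests, 1 - 0.95^2 = 9.75%.

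| Covariates | One scan, Wald | One scan, LR | Either of two, Wald | Either of two, LR |
|---|---|---|---|---|
| 0 | 3.9% | 5.9% | 7.7% | 11.6% |
| 3 | 4.0% | 6.4% | 8.6% | 13.3% |
| 5 | 4.9% | 8.9% | 8.9% | 17.1% |

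So the excess comes mainly from having two chances. Small-sample inflation of the test itself appears under the likelihood-ratio (LR) test and not under Wald.

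**If more is tried than 2b names:**
- Six candidates (2 scans x Ki, SUV1, SUV2), correlation 0.5 to 0.8 within a scan, fixed covariates: 16-22% Wald, 21-37% LR. For six independent exact tests, 1 - 0.95^6 = 26.5%.
- One FLT predictor, any subset of up to three of five covariates: 12% Wald, 18% LR.
- Two predictors, any subset of up to two of five covariates: 18% Wald, 25% LR.
- Six candidates, any subset of up to two of four covariates: 31% Wald, 41% LR.

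**After the fix.** Two FLT predictors (one measure, two scans), fixed covariates, Firth-penalised likelihood-ratio test, Bonferroni 0.025 each, 10,000 runs: any false finding 4.6%, 4.7% and 4.5% with 1, 2 and 5 covariates. Bonferroni with an unpenalised LR test gave 6.3%, 7.4% and 10.0%.

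**The case against.** The strongest reply is that 2b makes no claim at all. It is a secondary objective worded as an evaluation, the sample-size section covers only the primary objectives, and 10.2.2 says results may be published as coming from pilot studies. Section 8.1.3 does not state maximum likelihood, a test or an alpha, and does not say that every known predictor must enter the model. The Ki, SUV1 and SUV2 comparison has its own objective (2c), and Table 3 lists recorded parameters rather than tests for 2b. Most of this stands. It limits the size of the finding and makes it a recommended change rather than an essential one.

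A reader might infer that the plan commits to a confirmatory claim whose false-positive risk is several times 5%. The documents do not support that. With the two named scans and a fixed model, the figure is 8-17%. Rates of 30-40% need six candidates with the likelihood-ratio test, or six candidates with a search over covariates, and none of these is written down.

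Two further points are fair. FLT is not one of the response criteria, so the problem with the post-therapy scan is its timing; the test result is not built into the outcome. And limiting adjustment has a price: in simulation, omitting one prognostic factor correlated with FLT (shared variance 25-50%, log-odds 0.5 to 1 per SD) gave 9-42% false positives by Wald and 13-48% by LR.

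What the reply does not remove is the estimation bias, which arises whatever label or test is used if the model is fitted by maximum likelihood. Nor does it supply a rule for the two scans.

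**Conclusion.** The point holds as a should-fix item for a secondary objective. With about 15 non-responders, maximum likelihood would on average overstate the adjusted FLT log-odds by about 17-49% with one to five covariates. This assumes a true log-odds of 1.0 per SD; the typical (median) overstatement is smaller. The chance that at least one of the two named scans is falsely significant is about 8-9% by Wald and 12-17% by likelihood ratio, if each is tested at 5%. That level, the covariate effects and the correlations are assumptions, because the documents give none of them. Higher rates are possible only through choices that the plan leaves open. Whatever the error rate, post-therapy uptake should not be called a predictor of a response assessed at about the same time.

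**What to change.** In 8.1.3, state the following for 2b:

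- **Model:** Firth-penalised logistic regression for complete response, with penalised-likelihood 95% confidence intervals.
- **FLT measure:** target-lesion 1-hour SUV. Treat Ki, 2-hour SUV and any larger model as exploratory.
- **Covariates:** one or two, fixed now, for the sponsor to choose. Histology, stage, previous therapy and ECOG status are already collected under 7.1. Treatment regimen is a candidate because 8.1.4 assumes response of 74% against 50%, an odds ratio of (0.74/0.26)/(0.50/0.50) = 2.85. The list in 7.1 names previous therapy but not the current regimen, so it would need an entry if regimen is chosen.
- **Two scans:** either Holm or Bonferroni over the pre- and post-therapy results, or an explicit exploratory label for 2b.
- **Wording:** report post-therapy uptake as an association concurrent with the response assessment.

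The cost is a few lines of text and a standard software option. Section 1.7 reports 8 of 40 patients enrolled in this arm at this version, so specifying the model now still has value. The downside is a narrower claim: independence would mean adjusted for the one or two named covariates only, with the risk from omitted factors described above. The simulated error rate stayed at about 4.5% with five covariates under Firth and Bonferroni, so a somewhat larger set could be defended on error rate if it is fixed in advance.

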8.1.4 Sample size

We plan to enroll 40 participants in the first arm and 30 participants in the residual tumor arm.

In the first arm, we assume that patients enrolled in this trial come from a randomized trial of DA-EPOCH-R vs. R-CHOP. With DA-EPOCH-R treatment, the expected response rate is 74%(92), while with R-CHOP it is 50%. (21). If we assume half of the patients enrolled in this trial will receive DA-EPOCH-R and the other half will receive R-CHOP, the average response rate is 62%, which will provide about 25 responders, who will contribute to estimates of sensitivity. About 15 patients will be non-responders and will contribute to estimates of specificity. The lower bounds for sensitivity are given in **Table 7**. Lower bounds for specificity are given in **Table 8**.

For the second primary objective, we assume that the 50% of patients with FDG positive residual disease will have positive pathology.(93) This provides 15 positives and 15 negatives. **Table 8** provides lower bounds for confidence intervals for sensitivity and specificity for this objective.

The following table provides expected lower bounds for 95% confidence intervals given observed values of sensitivity and specificity for a sample size of 15. We anticipate sensitivity and specificity to be about 85% and 90%, respectively. Hence, the sample size will provide lower bounds above the chance threshold of 50%.

Table 7

Sensitivity (n=25)	Expected lower bound of exact 95% CI
20/25(=.80)	0.59
21/25(=.84)	0.64
22/25(=.88)	0.69

Table 8

Sensitivity/Specificity (n=15)	Expected lower bound of exact 95% CI
12/15 (=0.8)	0.52
13/15 (=0.87)	0.60
14/15 (=0.93)	0.68

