7.2.1 Early Treatment Arm

Overall response will be assessed according to the Cheson revised response criteria, 2007.(91). This data will be collected under the therapy trial in which the patient is also enrolled. For primary analyses, CR and CRu will be considered positive for response.

Table 6 Summary of the response criteria

Response	Definition	Nodal Masses	Spleen, Liver	Bone Marrow
CR	Disappearance of all evidence of disease	(a) FDG-avid or PET positive prior to therapy; mass of any size permitted if PET negative (b) Variably FDG-avid or PET negative; regression to normal size on CT	Not palpable, nodules disappeared	Infiltrate cleared on repeat biopsy; if indeterminate by morphology, immunohistochemistry should be negative
PR	Regression of measurable disease and no new sites	≥ 50% decrease in SPD of up to 6 largest dominant masses; no increase in size of other nodes (a) FDG-avid or PET positive prior to therapy; one or more PET positive at previously involved site (b) Variably FDG-avid or PET negative; regression on CT	≥ 50% decrease in SPD of nodules (for single nodule in greatest transverse diameter); no increase in size of liver or spleen	Irrelevant if positive prior to therapy; cell type should be specified
SD	Failure to attain CR/PR or PD	(a) FDG-avid or PET positive prior to therapy; PET positive at prior sites of disease and no new sites on CT or PET (b) Variably FDG-avid or PET negative; no change in size of previous lesions on CT		
Relapsed disease or PD	Any new lesion or increase by ≥ 50% of previously involved sites from nadir	Appearance of a new lesion(s) > 1.5 cm in any axis, ≥ 50% increase in SPD of more than one node, or ≥ 50% increase in longest diameter of a previously identified node > 1 cm in short axis Lesions PET positive if FDG-avid lymphoma or PET positive prior to therapy	> 50% increase from nadir in the SPD of any previous lesions	New or recurrent involvement

Abbreviations: CR, complete remission; FDG, [¹⁸F]fluorodeoxyglucose; PET, positron emission tomography; CT, computed tomography; PR, partial remission; SPD, sum of the product of the diameters; SD, stable disease; PD, progressive disease.

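### Section 8.1.4 sizes early-arm sensitivity on the 25 expected responders and specificity on the 15 non-responders, the reverse of the analysis plan in 8.1.3

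*Combined protocol and SAP*

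**What the plan says.** All references are to the combined protocol and SAP.

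- **Section 8.1.4, group sizes.** "We plan to enroll 40 participants in the first arm and 30 participants in the residual tumor arm". For the first arm the response rates are 74% with one regimen and 50% with the other. With half the patients on each, the average is 62%.
- **Section 8.1.4, assignment.** The average rate gives the split "which will provide about 25 responders, who will contribute to estimates of sensitivity". Then: "About 15 patients will be non-responders and will contribute to estimates of specificity". Table 7 is accordingly headed as sensitivity with n=25. Table 8 (n=15) is headed for both measures and serves early-arm specificity and the whole residual-mass arm.
- **Section 8.1.3, definitions.** FLT uptake above mediastinal blood pool is test positive. In the early-response arm, patients with CR or CRu "will be considered disease negative (all others will be considered disease positive".
- **Section 7.2.1.** "For primary analyses, CR and CRu will be considered positive for response".
- **Section 8.1.4, conclusion.** With sensitivity and specificity anticipated at about 85% and 90%: "Hence, the sample size will provide lower bounds above the chance threshold of 50" per cent.

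**The concern.** Section 8.1.3 fixes both axes of the early-arm two-by-two table. Sensitivity is the proportion test positive among the disease positive, and the disease positive are the non-responders. Specificity is the proportion test negative among the disease negative, and those are the complete responders. Section 8.1.4 puts each group under the other measure.

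Two things are at stake. First, the precision offered for a primary endpoint rests on the wrong denominator: sensitivity is presented as estimated in 25 patients when the analysis plan gives it about 15. Second, two subsections of the same statistical chapter disagree on what sensitivity means in this arm. The residual-mass arm takes malignancy as the positive state. Following the 8.1.4 assignment would therefore give the word opposite meanings in the two primary objectives.

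**Working it through.** **Inputs.** From 8.1.4: arm size 40, response rates 74% and 50%, exact 95% intervals, anticipated sensitivity 85% and specificity 90%. From 8.1.3: the definitions of disease status and test positivity.

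**Step 1. Group sizes.** (0.74 + 0.50)/2 = 0.62. Responders: 40 × 0.62 = 24.8, about 25. Non-responders: 40 × 0.38 = 15.2, about 15. This agrees with the plan.

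**Step 2. Reproduce Tables 7 and 8.** The two-sided Clopper-Pearson lower bound for x out of n is the 0.025 quantile of Beta(x, n − x + 1).

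| Result | Plan | Recomputed |
|---|---|---|
| 20/25 | 0.59 | 0.593 |
| 21/25 | 0.64 | 0.639 |
| 22/25 | 0.69 | 0.688 |
| 12/15 | 0.52 | 0.519 |
| 13/15 | 0.60 | 0.595 |
| 14/15 | 0.68 | 0.681 |

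All six entries reproduce. A one-sided 95% bound does not match (for example, 0.67 at 21/25). The bounds are right, so the question is only which measure each n belongs to.

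**Step 3. Orientation.** Under 8.1.3, sensitivity = P(FLT positive | not CR/CRu), with n about 15. Specificity = P(FLT negative | CR/CRu), with n about 25. Applying the 8.1.4 assignment with the same positivity rule would make sensitivity equal to P(FLT positive | CR/CRu). That is a false-positive rate, which an anticipated 85% cannot describe.

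**Step 4. Lower bounds near the anticipated values.**
- Sensitivity near 85%: 21/25 gives 0.639 as printed; 13/15 gives 0.595 under 8.1.3. These are observed rates of 84% and 87%, so the gap is slightly understated. At an equal 80% the figures are 0.593 (20/25) and 0.519 (12/15).
- Averaged over the binomial distribution at a true 85%, the interval width is 0.30 with n=25 and 0.38 with n=15.
- Specificity near 90%: 13/15 to 14/15 gives 0.595 to 0.681 as printed; 22/25 to 23/25 gives 0.688 to 0.740 under 8.1.3.

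**Step 5. Chance that a lower bound exceeds 0.50.** The smallest qualifying counts are 12/15 (0.519; 11/15 gives 0.449) and 18/25 (0.506; 17/25 gives 0.465). The chance is the binomial upper tail from that count.

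| | As in 8.1.4 | Under 8.1.3 |
|---|---|---|
| Sensitivity, true 85% | n=25: P(X ≥ 18) = 0.9745 | n=15: P(X ≥ 12) = 0.8227 |
| Specificity, true 90% | n=15: P(X ≥ 12) = 0.9444 | n=25: P(X ≥ 18) = 0.9977 |
| Both, fixed 15/25 split | 0.9745 × 0.9444 = 0.920 | 0.8227 × 0.9977 = 0.821 |

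The product is valid because the two groups contain different patients. The joint chance falls because the lower anticipated value, 85%, now sits on the smaller group.

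**The case against.** **The 8.1.4 orientation could be deliberate.** Section 7.2.1 calls CR/CRu positive for response, and the primary objective speaks of FLT as an indicator of complete response. If response were the target condition, responders would belong to sensitivity. That is a coherent convention, but it needs low uptake to be the positive test, and no section says so. Sections 5.1.2, 5.5.2 and 8.1.3 all make high uptake positive, although they differ on the reference background. What stands is that 7.2.1 does not contradict 8.1.3: a patient can be positive for response and negative for disease. It needs a clarifying phrase only.

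**The authors may have had the groups in mind, not the labels.** If the 85% was meant for the 25 responders and the 90% for the 15 non-responders, renaming the measures leaves the chances at 0.9745 and 0.9444, and nothing is lost. The documents give the two values by measure, so they are read that way here, but the possibility cannot be excluded.

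**A reader might infer that the plan fails to deliver bounds above 50%.** The documents do not support that. Section 8.1.4 presents the bounds as conditional on observed values, and Table 8 already prints 0.52 at 12/15 and 0.60 at 13/15. The sentence survives the exchange at the anticipated values. The chance of clearing 0.50 is a useful addition for an estimation study, but the plan did not promise it.

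**A reader might also infer that the published measures will come out exchanged.** That would happen only if an analyst followed 8.1.4 over 8.1.3, and 8.1.3 is the analysis plan and is explicit.

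**Other effects are separate.** The residual-mass arm is planned at 15 and 15, so the exchange does not touch it. A response rate other than 62% would change the number of non-responders, but the exchange does not cause that dependence.

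**Conclusion.** The contradiction between 8.1.3 and 8.1.4 is real and concerns a primary endpoint. It is an inconsistency of assignment: the group sizes and all six tabulated bounds are correct.

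With 8.1.3 standing, the stated precision for early-arm sensitivity is too favourable and that for specificity too unfavourable. The net effect is a moderate loss of about 10 percentage points in the chance that both lower bounds exceed 0.50 (92% to 82%). This does not amount to a failed sample size, and the 50% statement remains true for any sensitivity result of 12/15 or better. At a true 85%, that leaves about an 18% chance (1 − 0.8227) of falling short.

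These figures assume a fixed 15/25 split, two-sided exact intervals, and that 85% and 90% apply to the early-response arm as sensitivity and specificity in the sense of 8.1.3. The need to reconcile the two sections does not depend on the last assumption; the size of the precision change does.

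**What to change.** Use one orientation throughout. Keeping 8.1.3 is the simplest course, because it matches the residual-mass arm and the written positivity rule. Then:

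1. In 8.1.4, state that the roughly 25 responders contribute to specificity and the roughly 15 non-responders to sensitivity.
2. Relabel Table 7 as specificity (n=25) and add a row for 23/25 (lower bound 0.74), since its present rows stop at 0.88, below the anticipated 90%.
3. Refer early-arm sensitivity to Table 8.
4. Add to 7.2.1 that CR/CRu counts as disease negative when sensitivity and specificity are computed.
5. Reword the closing sentence of 8.1.4 as conditional on observing about 85% and 90%, and note that n=15 needs at least 12/15.

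The cost is a few sentences, one table label and one table row, with a slightly less favourable stated precision for sensitivity. Enrolment does not change. Section 1.7 reports 8 of 40 early-arm patients enrolled at 1 March 2013, so the correction can be made well before the analysis.

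### Section 8.1.4 turns lower bounds that depend on the observed counts into an unconditional assurance for the residual-mass arm. At the anticipated accuracy the bound clears 50% with probability about 82% (sensitivity) and 94% (specificity).

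*Combined protocol and SAP*

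**What the plan says.** Section 8.1.4 of the combined protocol and SAP sets the sizes: "We plan to enroll 40 participants in the first arm and 30 participants in the residual tumor arm". For the second primary objective, "we assume that the 50% of patients with FDG positive residual disease will have positive pathology", and from this, "This provides 15 positives and 15 negatives".

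It then introduces Table 8: "The following table provides expected lower bounds for 95% confidence intervals given observed values of sensitivity and specificity for a sample size of 15". The column is headed "Expected lower bound of exact 95% CI" and has three rows: 12/15 (0.52), 13/15 (0.60) and 14/15 (0.68). The text continues "We anticipate sensitivity and specificity to be about 85% and 90%, respectively", and concludes "Hence, the sample size will provide lower bounds above the chance threshold of 50" percent.

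Section 8.1.3 gives the planned analysis: "For the primary analyses, sensitivity and specificity will be estimated and 95% confidence intervals provided". It states no hypothesis test, power or success criterion.

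**The concern.** Each row of Table 8 answers a conditional question: if this count is observed, where does the lower bound fall? The closing sentence answers a different one, namely what the sample size will deliver if FLT performs as anticipated. Moving from one to the other treats the observed proportions as equal to the anticipated true values and the split as exactly 15 and 15. Neither is fixed by the design.

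Table 8 also begins at 12/15, the lowest count whose bound exceeds 50%, so the reader sees no outcome that falls short.

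The sentence is the plan's only stated conclusion on whether 30 patients are enough for primary objective 1.b. At stake is how firmly that assurance may be read. The estimates and intervals to be reported are not affected.

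**Working it through.** **Inputs, all from section 8.1.4.** Arm size 30; prevalence of positive pathology 50%, hence 15 positives and 15 negatives; anticipated sensitivity 0.85 and specificity 0.90; exact 95% interval; threshold 0.50.

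**Step 1: reproduce Table 8.** The two-sided exact (Clopper-Pearson) lower bound for x correct out of n is the 2.5% quantile of a Beta(x, n − x + 1) distribution. For n = 15:

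| Correct | Lower bound | Table 8 |
|---|---|---|
| 11/15 | 0.449 | not shown |
| 12/15 | 0.519 | 0.52 |
| 13/15 | 0.595 | 0.60 |
| 14/15 | 0.681 | 0.68 |
| 15/15 | 0.782 | not shown |

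The stated entries all agree after rounding. Table 7 (n = 25) also reproduces: 0.593, 0.639 and 0.688 against 0.59, 0.64 and 0.69.

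**Step 2: find the count needed.** Since 11/15 gives 0.449 and 12/15 gives 0.519, the bound exceeds 0.50 only with at least 12 correct out of 15.

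**Step 3: chance of reaching that count at the anticipated values, 15 per group.** Sum the Binomial(15, p) probabilities for 12, 13, 14 and 15 correct.

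- Sensitivity, p = 0.85: 0.218 + 0.286 + 0.231 + 0.087 = 0.823 after rounding.
- Specificity, p = 0.90: 0.129 + 0.267 + 0.343 + 0.206 = 0.944 after rounding.
- Both, from different and hence independent patients: 0.823 × 0.944 = 0.777.

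A one-sided 95% exact bound or a Wilson bound leaves these three figures unchanged, because the count needed stays at 12.

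**Step 4: average lower bound.** Weighting the exact lower bound at each count by its binomial probability gives 0.583 at p = 0.85 and 0.644 at p = 0.90. On average, then, both bounds exceed 0.50.

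**Step 5: sensitivity calculation for the split.** Take the number of positives as Binomial(30, 0.5), with all 30 patients evaluable. Under that model an exact 15/15 split has probability C(30, 15)/2^30 = 0.14. Recompute the count needed for each group size and average over the splits: 0.761 for sensitivity, 0.900 for specificity, 0.679 for both. Two neighbouring splits show the effect:

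- 14 positives and 16 negatives: 0.648 × 0.932 = 0.604.
- 16 positives and 14 negatives: 0.790 × 0.842 = 0.665.

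The joint 0.679 depends on the interval method. It would be 0.774 with Wilson and 0.811 with a one-sided 95% exact bound. The two-sided exact interval is used here because it is the one that reproduces the plan's tables.

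**The case against.** The strongest reply is that the passage carries its own condition. Table 8 is introduced as conditional on observed values and its column refers to expected bounds. Read in sequence, the text says that if the observed values come out near 85% and 90%, the bounds lie above 50%. That is true: 13/15 and 14/15 give 0.60 and 0.68. It is also true of the average bounds. Sizing a small estimation study by expected interval limits is ordinary practice, and section 8.1.3 promises only estimates with intervals.

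Most of this stands. It disposes of several stronger inferences a reader might draw:

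- *That the tables are miscalculated.* They are not.
- *That the plan claims certainty.* The sentence can be read as a loose statement about expected bounds, so attributing a 100% claim to it goes beyond the text.
- *That the arm fails in about one trial in four to one in three, and that such a result would count against FLT.* The documents contain no rule that both bounds must exceed 50%, no power target and no go/no-go decision. An observed 11/15 would be reported with its interval, and nothing would be declared failed. The joint 78% and 68% are answers to a criterion added here for illustration.
- *That 68% follows from the plan alone.* The plan states 50% prevalence and a 15/15 split. Binomial variation around that split is an added, though reasonable, assumption.

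What the reply does not rescue is the wording of the conclusion. It says what the sample size will provide, not where the bounds lie on average, and no probability is given anywhere.

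**Conclusion.** Wrong as written, minor. The step from bounds at given counts to an unconditional assurance is not valid. If true sensitivity is 85% and true specificity 90%, with 15 evaluable patients per group, the two-sided exact 95% lower bound exceeds 50% with probability about 82% and 94% respectively. What can be said without qualification at those values is that the average bounds, about 0.58 and 0.64, are above 50%.

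The 82% and 94% rest only on the plan's anticipated values and its 15/15 split. The figures for a varying split (76%, 90%, and 68% for both) also assume a binomial number of positives and 30 evaluable patients. The documents give no figure for non-evaluable patients, although section 5.3 says biopsy is not indicated in many of them and relies on clinical follow-up instead.

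A reader might infer that the arm is too small for its purpose. The documents do not support that: the stated purpose is estimation, and no precision or power target is missed.

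**What to change.** In section 8.1.4, replace the concluding sentence for the residual-mass arm with wording such as:

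*If true sensitivity is 85% and specificity 90%, the probability that the exact 95% lower bound exceeds 50% is about 82% and 94% respectively with 15 evaluable patients per group (about 78% for both together; illustrative, as no joint success rule is set).*

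Add the 11/15 row (lower bound 0.45) to Table 8, so that the point where the bound falls below 50% is visible.

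As a sensitivity figure, add about 76%, 90% and 68% (both), labelled as assuming 30 evaluable patients, a Binomial(30, 0.5) split and the two-sided exact interval.

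The cost is two sentences and one table row, and a less favourable stated assurance. Enrolment, procedures and analysis stay the same. Section 1.7 reports 22 of 30 patients already in this arm, so the restatement is best made before the data are analysed.
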